#### 9.4.3.2 Secondary Objective – Dose Proportionality

Dose proportionality for  $AUC_{inf}$ ,  $AUC_t$ , and  $C_{max}$  will be evaluated using the power model (including all doses) and also using an ANOVA model where each dose will be compared with a reference dose in a pairwise basis. The mean slope from the power model and the set of pairwise comparisons from the ANOVA method will constitute descriptive evaluations of dose proportionality.

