**Equation 2:**

$$Y_{ik} = \alpha \times \text{Dose}^{\beta}$$

where  $\alpha$  includes the error.

Dose proportionality for PK parameters will be assessed by restricted maximum likelihood using SAS PROC MIXED. The mean slope will be estimated from the power model and the corresponding 90% CI calculated. If the 90% CI of the slope of the  $C_{max}$  and AUCs contains 1, then dose proportionality is indicated.

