## 16.0 Pharmacokinetic Variables

### 16.1.1 Plasma Variables

- Plasma concentrations of galidesivir.
- Plasma PK parameters of galidesivir.

Venous blood samples will be collected to determine the plasma concentrations of BCX4430. The plasma concentration summaries and figures with mean values described in this section will be created using the safety population. The plasma PK parameter summaries and statistical analyses described in this section will be created using the PK population.

Plasma PK Parameters		
Parameter	Description	Programming Notes
AUC inf	Area under the concentration versus time curve extrapolated to infinite time, calculated as $AUC_{last} + (C_{last}/\lambda_z)$	AUCINF_obs from WNL  If valid lambda_z is not present, then parameter is flagged in listings and will not be used in summary statistics.
AUC t	Area under the concentration versus time curve from time zero to time "t"; may be denoted as AUC last if the "t" is the last timepoint with a measurable concentration	AUClast from WinNonlin If actual time deviates >20% from nominal time, then AUC t will be flagged in listings and will not be used in statistical analyses. If valid $\lambda_z$ is not present, then AUC t is flagged in listings and will not be used in statistical analyses.
% AUC exp	Percentage of AUC extrapolated between AUC last and AUC inf	AUC_%Extrap_obs from WinNonlin Listed only
C last	Last measurable concentration of drug	Clast from WinNonlin If actual time at T last deviates >20% from nominal time, then parameter is flagged in listings and will not be used in summary statistics.
T last	Time of last measurable concentration of drug	Tlast from WinNonlin If actual time at T last deviates >20% from nominal time, then parameter is flagged in listings and will not be used in summary statistics
C max	Maximum observed concentration of drug	C max from WinNonlin

Plasma PK Parameters		
Parameter	Description	Programming Notes
$t_{1/2}$	Estimate of the terminal elimination half-life of the drug	HL_Lambda_z from WinNonlin  If valid $\lambda_z$ is not present, then parameter is flagged in listings and will not be used in summary statistics.
CL	CL = Dose/AUC where "Dose" is the dose of the drug and AUC = AUC inf	CL_obs from WinNonlin

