$\lambda_z$	Terminal elimination rate constant, estimate by linear regression of the terminal elimination phase of the concentration of drug versus time curve	Lambda_z from WinNonlin  If Rsq < 0.80 then parameter is flagged in listings and will not be used in summary statistics.
$V_z$	Volume of distribution of the drug	Vz_obs from WinNonlin  If valid $\lambda_z$ is not present, then parameter is flagged in listings and will not be used in summary statistics.
$T_{max}$	Time to $C_{max}$	Tmax from WinNonlin

Note: In all derivations of PK parameters, BQL values at the beginning of the profile will be set to zero, whereas BQL values that occur after the first quantifiable point will be considered missing. Samples that are BQL but are between two samples with detectable concentrations will be excluded from PK analysis.

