### 16.2.4 Dose Proportionality Analyses

#### 16.2.4.1 Power Model

The assessment of dose proportionality for the PK parameters of BCX4430 will use a power model approach (including all doses). A model with ln-transformed dose (dose continuous) as a fixed effect and subject as a random effect will be applied to the following ln-transformed PK parameters: AUCt, AUCinf, and Cmax. Although there is no formal statistical hypothesis tested for this secondary objective, there will be evidence for dose-proportionality for each PK parameter if the 90% confidence interval (CI) of the fixed slope for ln-dose contains 1. No adjustment for multiplicity will be performed for the set 3 of PK parameters.

The SAS pseudo code for the power model is as follows:

```
data adpp;
set adpp;
ln_auc = log(auc);
ln_dose = log(dose);
run;

proc mixed data=adpp method=reml;
by parameter;
class subject;
model ln_auc = ln_dose / ddfm=kr ci alpha=0.1;
random subject;
run;
```

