#### 16.2.4.2 ANOVA Model Pairwise Comparisons

Following log-e transformation, dose-normalized PK parameters will be analyzed with an ANOVA model using PROC MIXED. Each dose will be compared with a reference dose on a pair-wise basis. Pairwise

comparisons of the ratio of GLS means and the corresponding 90% CI will be estimated for each PK parameter of interest. Although there is no formal statistical hypothesis tested for this secondary objective, if the 90% CI for the geometric LSM ratio falls completely within the 0.8 to 1.25 equivalence region then dose proportionality is indicated for the specific comparison. No adjustment for multiplicity will be performed for the set of descriptive pairwise comparisons.

The SAS PROC MIXED pseudo code for the pairwise comparison for the ANOVA model is as follows:

```
data adpp;
set adpp;
ln_auc_dose = log(auc)/dose;
run;

ods output diffs=diffs;
ods output lsmeans=lsmeans;
proc mixed data=adpp method=reml;
by parameter;
class dose;
model ln_auc_dose = dose / ddfm=kr;
lsmeans dose / pdiff alpha=0.1 cl;
run;
```

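### AUCt for dose proportionality is programmed as AUClast with no common end time, so its slope can be biased above 1 if the assay's lower limit exceeds late concentrations at low doses

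*SAP*

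**What the plan says.** The AUCt row of SAP 16.1.1 describes an area to a time t and lets it be called AUClast when t "is the last timepoint with a measurable concentration". The programming note beside it makes that the only case: AUCt is "AUClast from WinNonlin". The note under the same table handles samples below the quantitation limit (BQL): early ones are set to zero, "whereas BQL values that occur after the first quantifiable point will be considered missing". Integration therefore stops at each subject's own last measurable sample.

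The only timing rule on AUCt begins "If actual time deviates >20% from nominal time, then" and leads to flagging and exclusion. It compares actual with scheduled time and does not give the cohorts a shared end point.

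The resulting AUCt, with AUCinf and Cmax, goes through two analyses. For the power model (SAP 16.2.4.1), "there will be evidence for dose-proportionality for each PK parameter if the 90% confidence interval (CI) of the fixed slope for ln-dose contains 1". For the pairwise ANOVA (SAP 16.2.4.2), if the 90% CI of the dose-normalised ratio "falls completely within the 0.8 to 1.25 equivalence region then dose proportionality is indicated". No fixed-interval AUC is among the three parameters. The documents give the assay's upper limit (10,000 ng/mL, in the Cohort 2 dose escalation summary filed with the SAP) but not its lower limit.

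**The concern.** A proportionality slope is meant to compare the same piece of the exposure curve at each dose. AUClast does this only if every cohort remains measurable to the same visit. After 96 h the samples are far apart: Day 6, 8, 14 and 21 (protocol 11.2.1), or nominally 120, 168, 312 and 480 h. If a low-dose subject drops below the limit one visit before a high-dose subject, a whole segment of area is lost at the low dose only. Under exact proportionality the low dose can reach the limit at the same visit or earlier, never later, so any resulting bias in the mean slope is upward.

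At stake is the reported conclusion for one of the three parameters. A departure from proportionality in AUCt could be partly a product of the assay limit and visit spacing. The SAP judges each parameter separately and does not say what to conclude if AUCt and AUCinf disagree.

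**Working it through.** The plan gives no figure to reproduce: there is no power calculation and no stated lower limit. The check asks what slope AUCt would show if the drug were exactly proportional.

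**Inputs**
- Cohort 2 dose escalation summary (10 mg/kg IV, interim geometric means): half-life 89.1 h, AUC0-24 20,400 ng·h/mL, AUCinf 32,400 ng·h/mL, CL 285 mL/h/kg, Vz 36,600 mL/kg; CV 14.1% for AUClast and 21.6% for half-life.
- Protocol Table 4: 24 h concentration of 134 ng/mL on Day 1 after 10 mg/kg IM.
- Doses 5, 10, 15 and 20 mg/kg, with 6 active subjects each.
- Assumption: a lower limit of 1 to 10 ng/mL.

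**Consistency check.** λz = ln 2 / 89.1 = 0.007779 per h, and CL/λz = 285/0.007779 ≈ 36,635 mL/kg, against 36,600 tabulated.

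**Concentration at 24 h, 10 mg/kg**, derived three ways:
- from AUCinf: (32,400 − 20,400) × 0.007779 = 93 ng/mL
- from CL: (10,000,000/285 − 20,400) × 0.007779 = 114 ng/mL
- IM trough: 134 ng/mL

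**Day 21 concentration.** Assuming mono-exponential decline after 24 h, C480 = C24 × exp(−0.007779 × 456) = C24 × 0.0288, scaled by dose:

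| Dose (mg/kg) | 5 | 10 | 15 | 20 |
|---|---|---|---|---|
| C480 (ng/mL) | 1.3–1.9 | 2.7–3.9 | 4.0–5.8 | 5.4–7.7 |

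A limit of 1 ng/mL or less leaves every cohort measurable to Day 21. A limit of 2 to 5 ng/mL separates the cohorts.

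**Worked case: limit 2 ng/mL, C24 = 93.** The 5 mg/kg cohort ends at 312 h and the others at 480 h. AUClast per mg/kg is 2,040 + 1,200 × (1 − exp(−0.007779 × 288)) = 3,112 at 5 mg/kg, and 2,040 + 1,200 × (1 − 0.0288) = 3,205 elsewhere. On ln dose, the 5 mg/kg point lies 0.795 below the mean, and the sum of squares over the four doses is 1.084. The slope is 1 + 0.795 × ln(3,205/3,112)/1.084 = 1.02.

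**Same calculation at other limits**, over the three C24 values:

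| Limit (ng/mL) | Slope, all subjects at typical half-life |
|---|---|
| 1 | 1.00 |
| 2 or 3 | 1.02–1.03 |
| 5 | 1.02–1.08 |
| 10 | 1.07–1.08 |

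The spread at 5 ng/mL reflects which visit each cohort just reaches or just misses.

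**Simulation with subject variation.** Exposure CV 14%, half-life CV 21.6%, 6 subjects per dose, least-squares slope with 22 df. Each subject contributes one value per parameter, so the random subject effect cannot be separated from residual error and least squares gives the slope. Ranges cover repeated simulations over the C24 values:

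| Limit (ng/mL) | Mean slope | 90% CI excludes 1 (nominal 10%) |
|---|---|---|
| 1 | 1.00 | about 10% |
| 2–3 | 1.01–1.02 | 10–13% |
| 5 | about 1.04 | 14–18% |
| 10 | about 1.07 | 25–30% |

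**With a common end time** (0–96 h or 0–168 h) the mean slope is 1.00 and the CI excludes 1 in about 10% of runs at any limit considered.

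**The case against.** The strongest reply is that little rests on this. SAP 9.4.3.2 calls the proportionality results descriptive, and no hypothesis is tested. The escalation exposure criterion uses AUC24, a fixed interval. AUCinf goes through the same two models and largely avoids truncation. Tlast is reported and the extrapolated percentage is listed, so unequal horizons would be visible to a careful reader. The AUCt definition also follows protocol Table 9. All of this stands and limits the consequence. It does not correct the AUCt rule, which still yields its own stated conclusion.

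The anchor is also interim. One subject had samples only to 24 h, and three Cmax values exceeded the assay's upper limit. The tabulated 11.1% extrapolation does not match 1 − 30,200/32,400 = 6.8%. This is why a range of C24 values is used.

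Two stronger readings are tempting but unsupported.
- A reader might set a bias of 0.08 against the CI half-width of about 0.094 (exposure CV 14% alone) and infer a much higher false-exclusion rate at 5–10 ng/mL. That cuts every subject in a cohort at the same visit. Subjects differ in half-life, which smooths the cut and widens the half-width to about 0.11.
- A reader might infer the lower limit from Study 101, where AUCt per mg/kg rose from 518/0.3 = 1,727 to 27,100/10 = 2,710. Cmax per mg/kg also rose, from 167/0.3 = 557 to 7,980/10 = 798, and truncation cannot affect Cmax. The protocol itself reports slightly more than proportional increases in all three parameters. The 4.44 h half-life at 0.3 mg/kg hints at a lost terminal phase, but it rests on 5 subjects with a CV of 74.8%, by another route, and on assuming the same assay.

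**Conclusion.** The point holds conditionally. The SAP's AUCt has no common horizon, and any truncation bias under true proportionality is upward. Whether it occurs depends on a lower limit that the documents do not give, so they do not support saying that AUCt is or will be biased. At about 1 ng/mL or lower the effect is negligible, and at 2–3 ng/mL it is close to nominal. At 5 ng/mL the mean slope is about 1.04, and at 10 ng/mL about 1.07, with the false-exclusion rate rising to 14–18% and 25–30%.

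These figures assume exact proportionality, mono-exponential decline after 24 h, the interim Cohort 2 half-life and CVs, and sampling at nominal times. The matter is a modest weakness in one of three secondary, descriptive parameters. It is worth correcting because the correction is cheap.

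**What to change.** - In SAP 9.4.3.2, 16.1.1 and 16.2.4, put an AUC over a common interval that is quantifiable in all cohorts through the power model and the ANOVA, and base the partial-AUC proportionality statement on it. AUC0-96h is a natural choice: predicted C96 at 5 mg/kg is about 27–38 ng/mL, above every limit tabulated here. SAP 16.1.2 already implies this area, because CLr uses a time-matched AUC and urine collection ends at 96 h.
- Keep AUClast as a descriptive or secondary parameter.
- State the assay's lower limit of quantitation.

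The cost is one partial-area setting and some SAP wording, with no new data. The drawback is that AUC0-96h omits roughly 21–26% of total exposure: 12,000 × exp(−0.007779 × 72)/32,400 = 21% with C24 = 93, and 26% with C24 = 134. AUCinf stays in the analysis and covers that tail.

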### 16.2.2 Plasma Pharmacokinetic Parameters

Plasma PK parameters for BCX4430 will be estimated using non-compartmental methods with WinNonlin®.

The plasma PK parameters will be estimated from the concentration-time profiles. In estimating the PK parameters, BQL values at the beginning of the profile will be set to zero. BQL values that occur after the first quantifiable point will be considered missing. Samples that are BQL but are between two samples with detectable concentrations will be excluded from PK analysis.

Actual sampling times, rather than scheduled sampling times, will be used in all computations involving sampling times. If the actual time or dose time is missing, the scheduled time may be substituted in order to calculate the PK parameter.

Determination of points to be included in  $\lambda_z$  range will follow the Guideline for Defining, Calculating and Summarizing Pharmacokinetic / Pharmacodynamic Parameters (EDSREP 009 R 01) and rule will be noted in table and listing footnotes.

Descriptive statistics (n, arithmetic mean, SD, arithmetic CV%, geometric mean, geometric CV%, median, min, and max) will be used to summarize the calculated PK parameters by treatment. For  $T_{max}$ ,  $T_{lag}$ , and  $T_{last}$ , only n, median, min, and max will be presented.

Individual PK parameters AUCt, AUCinf, and Cmax with corresponding geometric means will be shown graphically for each treatment.

All individual subject PK parameters will be listed by treatment and period.

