## Appendix 3: List of End of Text Outputs

List of End of Text Tables and Figures:		
Output	Title	Analysis Population
Section 14.1 – Disposition and Demographic Data		
Table 14.1.1	Summary of Subject Disposition	All Subjects
Table 14.1.2.1	Summary of Demographics	Safety
Table 14.1.2.2	Summary of Demographics	PK
Table 14.1.3	Summary of Study Drug Administration	Safety
Section 14.2 – Plasma Pharmacokinetic Data		
Table 14.2.1	Summary of BCX4430 Plasma Concentrations	Safety
Table 14.2.2	Summary of BCX4430 Plasma Pharmacokinetic Parameters	PK
Table 14.2.3	Summary of BCX4430 Urine Pharmacokinetic Parameters	PK
Table 14.2.3.1	Statistical Analysis of the Dose Proportionality: Power Model	PK
Table 14.2.3.2	Statistical Analysis of the Dose Proportionality: ANOVA Model of Pairwise Comparisons	PK
Figure 14.2.4	Plot of Mean ( $\pm$ SD) BCX4430 Plasma Concentrations vs Time on a Linear Scale	Safety
Figure 14.2.5	Plot of Mean BCX4430 Plasma Concentrations vs Time on a Semi-Log Scale	Safety
Figure 14.2.6	Plot of Median BCX4430 Plasma Concentrations vs Time on a Linear Scale	Safety
Figure 14.2.7	Plot of Individual BCX4430 Plasma Concentrations vs Time on a Linear Scale	Safety
Figure 14.2.8	Plot of Individual BCX4430 Plasma Concentrations vs Time on a Semi-Log Scale	Safety
Figure 14.2.9	Scatter Plot of Individual BCX4430 Plasma Pharmacokinetic Parameters	PK
Section 14.3 – Safety Data		
Table 14.3.1.1	Summary of Adverse Events	Safety
Table 14.3.1.2	Summary of Treatment Emergent Adverse Events by System Organ Class and Preferred Term	Safety
Table 14.3.1.3	Summary of Treatment Emergent Adverse Events by Relationship to BCX4430	Safety
Table 14.3.1.4	Summary of Treatment Emergent Adverse Events by Severity	Safety
Table 14.3.2	Listing of Serious Adverse Events	All Subjects
Table 14.3.3	Listing of Deaths	All Subjects
Table 14.3.4	Listing of Abnormal Laboratory Values	All Subjects
Table 14.3.5.1	Summary of Laboratory Results	Safety
Table 14.3.5.2	Summary of Laboratory Shifts from Baseline	Safety

Table 14.3.5.3	Summary of Treatment Emergent Graded Laboratory Toxicities	Safety
Table 14.3.6	Summary of Vital Signs	Safety
Table 14.3.7.1	Summary of 12-Lead Electrocardiogram Results	Safety
Table 14.3.7.2	Summary of QTcF Categorical Findings	Safety

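### SAP 16.1.1 removes AUCt from the dose-proportionality models when lambda_z is not valid, although AUCt does not use lambda_z; the matching AUCinf rule does not clearly reach the models

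*SAP*

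**What the plan says.** The plasma parameter table in SAP 16.1.1 attaches a programming note to each parameter.

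- **AUCt** is taken as AUClast from WinNonlin. If a valid lambda_z "is not present, then AUC t is flagged in listings and will not be used in statistical analyses".
- **AUCinf** is AUClast + Clast/lambda_z. Its note reads: "If valid lambda_z is not present, then parameter is flagged in listings and will not be used in summary statistics".
- **t1/2 and Vz** carry the same note as AUCinf. **CL**, defined as Dose/AUCinf, carries no lambda_z condition.
- **lambda_z** itself: "If Rsq < 0.80 then parameter is flagged in listings and will not be used in summary statistics". This is the only validity criterion printed. For the choice of points in the terminal fit, SAP 16.2.2 "will follow the Guideline for Defining, Calculating and Summarizing Pharmacokinetic / Pharmacodynamic Parameters (EDSREP 009 R 01"), which is not among the documents.

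The power model in SAP 16.2.4.1 takes the "ln-transformed PK parameters: AUC t , AUC inf , and C max" and adds no exclusion of its own. Neither does the ANOVA in 16.2.4.2. SAP 10.2 keeps in the PK population anyone with at least one estimable parameter. Protocol 12.3.1.4 and 12.3.1.5 attach no lambda_z condition to AUCt, and SAP 7.1 declares no changes from the protocol.

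**The concern.** An area up to the last measurable concentration does not become unreliable because the terminal slope was poorly fitted. AUCinf does, because its extrapolated part is divided by that slope. The AUCt rule therefore removes from the power model and the pairwise ratios the AUC that stays sound when the terminal phase is poor, and nothing later in the SAP or in the protocol puts it back.

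If the AUCinf note is taken at its word, the summary table and the models for the same parameter could also rest on different subjects. Dose proportionality is a named secondary endpoint with six active subjects per dose, so each exclusion has a visible, if modest, cost in precision.

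**Working it through.** The documents give no power or precision figure for this analysis, so there is none to reproduce. The check is a reading of the text followed by sizing.

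**1. Text.** SAP 16.1.1 names two kinds of output: "The plasma PK parameter summaries and statistical analyses described in this section will be created using the PK population". SAP Appendix 3 titles Table 14.2.2 "Summary of BCX4430 Plasma Pharmacokinetic Parameters" and Table 14.2.3.1 "Statistical Analysis of the Dose Proportionality: Power Model". On that usage, a subject whose lambda_z is fitted with Rsq below 0.80 is
- in the AUCt summary but out of the AUCt models;
- out of the AUCinf summary but in the AUCinf models.

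If no lambda_z is fitted, AUCinf does not exist and only the AUCt line applies.

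**2. Precedent.** In protocol Table 3 (Study BCX4430-101, Part 1), one subject at 0.3 mg/kg and one at 0.75 mg/kg lost t1/2 on R-squared, leaving n = 5 in each cohort. AUCt is still reported with n = 6 in both.

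**3. One AUCt lost: pairwise ratios.** Four cohorts of 6, pooled variance, sigma = SD on the log scale. The 90% CI half-width is t(0.95, df) × sigma × sqrt(1/n1 + 1/n2).
- Full data: 1.725 × sqrt(2/6) = 0.996 sigma (20 df).
- One lost: 1.729 × sqrt(1/5 + 1/6) = 1.047 sigma (19 df), or 5% wider.

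For the chance that the CI lies within 0.80 to 1.25, assume exact proportionality, log(AUC/dose) as the response, and sigma² = ln(1 + CV²). The CV of 14.1% is for AUClast in the 10 mg/kg dose-escalation report bound with the SAP. The CVs of 12.0% and 17.7% are for AUCt at 7 and 10 mg/kg IM in protocol Table 3.

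| CV | Full data | One lost |
|---|---|---|
| 12.0% | 86% | 81% |
| 14.1% | 69% | 62% |
| 17.7% | 37% | 30% |

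**4. One AUCt lost: power-model slope.** The half-width is t(0.95, n−2) × sigma / sqrt(Sxx), with x = ln(5, 10, 15, 20) and 6 subjects per dose.
- Full data: Sxx = 6.505, half-width 1.717/sqrt(6.505) = 0.673 sigma.
- One lost at 5, 10, 15 or 20 mg/kg: 0.712, 0.675, 0.680 or 0.694 sigma, an increase of 5.7%, 0.3%, 1.0% or 3.1%.

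**5. One poorly based AUCinf kept.** If lambda_z is estimated at k times its true value and a fraction e of AUCinf is extrapolated, AUCinf is multiplied by (1 − e) + e/k. Take k = 0.5, so the factor is 1 + e. The size of this error is plausible: at Rsq = 0.80 the relative standard error of lambda_z is sqrt(0.2/(0.8 × (n − 2))), which is 50% with 3 points and 35% with 4.
- Interim value, e = 11.1% (10 mg/kg report): factor 1.111. The geometric mean of six moves by 1.111^(1/6) = 1.018, or 1.8%.
- With late samples, assume mono-exponential decline after 24 h, using that report's t1/2 of 89.1 h, AUC0-24 of 20400 and AUCinf of 32400. Then e(T) = (12000/32400) × exp(−ln 2 × (T − 24)/89.1). This is 3.9% at 312 h (Day 14) and 1.1% at 480 h (Day 21). The cohort mean moves by 1.039^(1/6) or 1.011^(1/6), that is 0.6% or 0.2%.

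**6. AUCt timing rule.** The AUCt row drops values whose actual time deviates by more than 20% from nominal but names no sample; the Clast and Tlast rows limit the rule to Tlast. Under the current protocol, with +1 day read as +24 h, Day 6 reaches 144/120 = 1.20, exactly 20% and so not over, and Day 8 reaches 192/168 = 1.143. SAP Appendix 2 still lists Days 5 and 7. Against its Day 5 time of 96 h, an on-time protocol Day 6 visit at 120 h is 25% late.

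**The case against.** A reader might infer that the SAP has the two exclusions exactly reversed: the sound measure out of the models and the fit-dependent one in. The strongest reply is that this needs both phrases to be read narrowly. The SAP defines neither summary statistics nor statistical analyses, and sections 9.4.3.2 and 16.2.4.2 call the dose-proportionality results descriptive. If the AUCinf note was meant to cover the models, AUCinf is barred too and the reversal disappears. A valid lambda_z is also not fully defined; the cited guideline may set an invalid fit to missing, in which case no AUCinf reaches the models. These points stand. The literal reading is the more natural one, but it is not certain.

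They do not rescue the AUCt sentence, which is unjustified on either reading.

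The other reply is that a lambda_z failure may never happen. In BCX4430-101, t1/2 was available in 24 of 24 subjects at 1.8 to 10 mg/kg. That is reassuring, but its R-squared threshold is printed as < 7, not 0.80, and dosing was IM, so an upper bound from 0 of 24 does not carry over to this rule.

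On timing, a reader might infer that permitted return visits breach the 20% rule under the current protocol. They do so only if +1 day is read as any time on the next calendar day.

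**Conclusion.** The AUCt rule is wrong as written and should be removed. The AUCinf gap is a probable but not established consequence of the wording, so the documents do not support calling the pair of rules reversed as a matter of fact.

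The effect is small and conditional on a lambda_z failure: a 5% wider pairwise CI per lost AUCt, a 69% to 62% fall in the chance of meeting 0.80 to 1.25 at CV 14.1%, and a shift in one cohort's mean AUCinf of 0.2% to 0.6% with quantifiable Day 14 to Day 21 samples (1.8% at the interim extrapolation). The probabilities assume exact proportionality and log(AUC/dose); the pseudo-code in SAP 16.2.4.2 prints log(auc)/dose instead. The assay's lower limit is not stated, so whether late samples are quantifiable is an assumption.

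Only a descriptive secondary analysis is touched. Cmax and the primary safety endpoints are not affected. The timing rule and the visit schedule are minor clarifications.

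**What to change.** Amend SAP 16.1.1 before database lock:

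- **AUCt:** delete the lambda_z sentence.
- **AUCinf, t1/2, Vz and CL:** use one rule. Without a valid lambda_z the parameter is flagged in listings and left out of both summary statistics and statistical analyses.
- **Definition:** state in the SAP what makes lambda_z valid, including any criterion taken from the cited guideline.
- **Minor:** limit the AUCt 20% rule to the actual time at Tlast, as in the Clast and Tlast rows, and align the Appendix 2 return visits (Days 5 and 7) with the protocol (Days 6 and 8).

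Separately, protocol 9.7 keeps a subject whose infusion is stopped mid-dose out of the PK population, while protocol 12.3.1.1 and SAP 10.2 do not mention this. The three passages must be reconciled.

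The cost is a few lines of SAP wording and one reconciled population definition. No new data are needed.

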**8.0 PK Summary (insert tables, appendices as allowed by sponsor, if available):**

Subjects in the table below have been anonymized with an alphabet code. Given the way the cohort dosing was staggered and that samples through only 24 hours post dosing were available for one subject in the cohort, only geometric mean data is presented in order to maintain the blind. If the subject received active, their half-life and clearance parameters are not included in the mean.

Additionally, the  $C_{max}$  for 3 subjects was greater than 10000 ng/mL (the upper limit of quantitation in the assay) and there was not time to re-assay prior to the dose escalation meeting. Therefore, it is possible that the AUC and  $C_{max}$  parameters are slightly underestimated. The anticipated geometric mean  $C_{max}$  for this cohort was approximately 10000-11000 ng/mL, so it is not anticipated that the  $C_{max}$  concentrations are much greater than 10000 ng/mL, or that the AUC parameters are significantly higher than calculated below.

[figure not shown]
No PK parameters met halting rules, and overall, the PK following a 10 mg/kg single dose administered by IV infusion was in line with anticipated exposure based on modeling and simulation and the exposure in Cohort 1 (5 mg/kg dose). Furthermore, the simulated exposure for the next two dose levels is not anticipated to exceed the PK stopping criteria in the protocol.

	T $\frac{1}{2}$ (h)	$C_{max}^*$ (ng/mL)	AUC 0-24h (ng.h/mL)	AUC 0-last (ng.h/mL)	AUC 0-inf (ng.h/mL)	%AUC extrap	Cl (mL/h/kg)	Vz (mL/kg)
Geomean	89.1	9240	20400	30200	32400	11.1	285	36600
%CV	21.6	10.6	12.8	14.1	20.9	41.5	14.2	35.4

\* 3 subjects had a  $C_{max}$  > 10000 ng/mL

The figure below shows the mean galidesivir concentration-time profiles for the first two cohorts of this study.

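### The CL row in SAP 16.1.1 lacks the lambda_z validity screen that AUCinf carries, although CL is Dose/AUCinf

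*SAP*

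**What the plan says.** The SAP 16.1.1 table gives each plasma parameter a definition and a programming note.

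- **AUCinf** is AUClast plus Clast/lambda_z. Its note includes: "If valid lambda_z is not present, then parameter is flagged in listings and will not be used in summary statistics". The t1/2 and Vz rows carry the same rule; the Vz row, for example, begins "Vz_obs from WinNonlin" and then adds it.
- **lambda_z** has its own acceptance threshold: "If Rsq < 0.80 then parameter is flagged in listings and will not be used in summary statistics".
- **CL** is dose over AUC; the row explains that the numerator "is the dose of the drug and AUC = AUC" with the subscript inf. Its complete programming note is "CL_obs from WinNonlin".

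SAP 16.2.2 then says that descriptive statistics "will be used to summarize the calculated PK parameters by treatment". It sets no general lambda_z condition. SAP 5.2.1 names CL among the secondary-endpoint PK parameters.

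**The concern.** CL depends on lambda_z only through AUCinf. If an AUCinf is too unreliable to summarise, dose divided by that AUCinf is unreliable for the same reason. The table screens the input and is silent on the output, and gives no reason for treating them differently.

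Two things are at stake. A named secondary parameter could include a value whose own denominator the SAP withholds. CL and AUCinf could also be summarised over different subjects in one table, so that a reader could not get from one to the other. With 6 active subjects per cohort, a single value has visible weight.

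**Working it through.** There is no design figure to reproduce, because the cohort size was not based on a calculation (SAP 6.1). The check is a reading of the table, followed by an illustration of size.

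**Step 1: dependence on lambda_z and screening, row by row (SAP 16.1.1).**

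| Parameter | Uses lambda_z? | Screened on valid lambda_z? |
|---|---|---|
| AUCinf | Yes, through Clast/lambda_z | Yes, summary statistics |
| t1/2 | Yes | Yes, summary statistics |
| Vz | Yes | Yes, summary statistics |
| CL | Yes, through AUCinf | No |
| % AUC extrapolated | Yes | Listed only, not summarised |
| AUCt | No | Yes, statistical analyses |

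CL is the only summarised plasma parameter that depends on lambda_z and has no screen.

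**Step 2: does another rule close the gap?**

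- SAP 10.2: the PK population needs only one estimable parameter, so a subject who fails on lambda_z stays in through Cmax or Tmax.
- SAP 9.4.1: no outlier analysis is planned.
- SAP 16.2.2: the guideline cited there is invoked for choosing the points in the lambda_z range. Its content is not in the documents.
- Protocol 12.3.1.4, Table 9: CL is defined in the same way, with no validity screen.

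None of these removes the CL value.

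**Step 3: when does it bite?** Only when lambda_z is estimated but its R-squared is below 0.80. If no lambda_z can be estimated, AUCinf and CL are both missing.

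**Step 4: size (illustration resting on an assumption).** Let five subjects have geometric mean CL equal to G, and let the sixth, unscreened subject have CL equal to r × G. The geometric mean of all six is G × r^(1/6), so the shift relative to the screened result is r^(1/6) − 1.

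- r = 0.5: 0.891 − 1 = −10.9%
- r = 0.75: 0.953 − 1 = −4.7%
- r = 1.5: 1.070 − 1 = +7.0%
- r = 2: 1.122 − 1 = +12.2%

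The range of r is assumed; the documents give no figure for it.

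**Step 5: frequency.** The documents give no rate for this trial. The nearest evidence is Study BCX4430-101 Part 1 (protocol 4.3.1.2, Table 3): t1/2 was reported for 6 of 6 subjects at each of 1.8, 4, 7 and 10 mg/kg, so 0 of 24 were excluded. The one-sided 95% upper bound is 1 − 0.05^(1/24) = 11.7% per subject. That study used IM dosing, and its printed R-squared threshold cannot be equated with 0.80, so this is only a rough guide.

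**The case against.** The strongest reply is that the SAP is silent; it does not direct inclusion. CL is defined from AUCinf, and a careful programmer could let the AUCinf exclusion carry over. The SAP also never states that a valid lambda_z means R-squared of at least 0.80; that is the natural reading of the lambda_z row. Both remarks are fair. A reader might infer that rejected values are certain to enter the CL summary, and the text does not support that. It does support the narrower statement that the row, followed as written, keeps them.

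The trigger also looks unlikely. Sampling runs to Day 21, which is 20 × 24 = 480 h after dosing, or 480/89.1 = 5.4 half-lives at the half-life in the Cohort 2 interim summary. A poor lambda_z affects CL only through the extrapolated piece of AUCinf, so where that piece is small the shift will be well inside the range above. Any mismatch would show in the reported n and in the flagged listings. These remarks limit the importance of the point but do not remove the inconsistency.

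Two stronger readings are tempting, and neither holds.

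- **The Cohort 2 interim summary as a measure of size.** Its geometric mean CL is 285 mL/h/kg, while 10,000,000 ng/kg ÷ 32,400 ng·h/mL = 309, an 8% difference. A reader might take this as the effect of the missing screen. The report says of one subject with only 24 h of samples that, if on active drug, "their half-life and clearance parameters are not included in the mean". There CL was to be dropped, which is the reverse of the present problem, and the reason was short sampling. The report does not say that the subject was on active drug, gives no n per column, and notes three Cmax values above the assay limit. The gap cannot be attributed to this cause.
- **The R-squared exclusions in Study BCX4430-101 as a rate.** They occurred at 0.3 and 0.75 mg/kg, well below the 5 to 20 mg/kg planned here. The 0 of 24 at 1.8 to 10 mg/kg is the closer comparison.

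**Conclusion.** The inconsistency is real and minor. As written, SAP 16.1.1 withholds an AUCinf that rests on a failed lambda_z but not the CL computed from it, and nothing elsewhere in the SAP or protocol corrects this. The conclusion rests on reading a valid lambda_z as one that meets the R-squared threshold.

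The frequency in this trial is unknown and probably low. If one subject of 6 is affected, and that CL is 0.5 to 2 times the others (assumed), the cohort geometric mean CL moves by about -11% to +12%. If no subject fails, nothing changes. CL is summarised descriptively only. Dose proportionality uses AUCinf, AUCt and Cmax (SAP 9.4.3.2 and 16.2.4), and the primary endpoints are safety and tolerability, so neither conclusion is affected.

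**What to change.** Add to the programming note of the CL row in SAP 16.1.1 the sentence already used for AUCinf: "If valid lambda_z is not present, then parameter is flagged in listings and will not be used in summary statistics".

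The cost is one line. It needs no new data or analysis and alters no result unless a subject fails the screen. It also settles before database lock which CL values are summarised. If the SAP is already closed, the same rule can go into the programming specification and be noted in the study report.
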